## 1. INTRODUCTION

Off-label prescription occurs when a practitioner chooses to prescribe a drug in a manner that is inconsistent with the prescribing information approved by the governing regulatory authority. For medicinal products approved by the European Commission, the licensed indications are documented in the Summary of Product Characteristics (SmPC). Examples of off-label prescribing may include, but are not limited to the administration of the drug in doses, routes of administration or for reasons outside of labeled indications, or use in patients who do not meet age requirements, or other criteria as outlined in the label.

### 1.1. Background and Rationale

Apixaban is an orally administered anticoagulant that inhibits coagulation factor Xa. It is currently approved for:

- 1) Prevention of venous thromboembolic events (VTE) in adult patients who have undergone elective hip or knee replacement surgery,
- 2) Prevention of stroke and systemic embolism in adult patients with nonvalvular atrial fibrillation (NVAf) with one or more risk factors,
- 3) Treatment of deep vein thrombosis (DVT) and pulmonary embolism (PE), and prevention of recurrent DVT and PE in adults.

These indications, referred to as knee and hip replacement, NVAf, and treatment of DVT/PE, along with the date of approval are shown in Table 1. Use of apixaban outside these indications is a regulatory and safety concern.

To address this concern, the Sponsor proposes two studies describing the utilization of the product in two countries of the European Union (EU): a drug utilization study focusing on off-label use of apixaban in Sweden, as described herein, and a second study of apixaban drug utilization in the Netherlands, which is described in a separate protocol.

The approved SmPC in Sweden will be used as the single reference safety document for this study.

**Table 1. Indications and Dates of EMA Authorisations**

	Abbreviated Indication	Indication	Date of EMA Authorisation
1.	THA/TKA	Prevention of VTE in adult patients who have undergone elective hip or knee replacement surgery	18 May 2011
2.	NVAf	Prevention of stroke and SE in adult patients with NVAf, with one or more risk factors, such as prior stroke or TIA; age $\geq$ 75 years; hypertension; diabetes mellitus; symptomatic heart failure (NYHA Class $\geq$ II).	19 Nov 2012
3.	Treatment of DVT/PE	Treatment of DVT and PE, and prevention of recurrent DVT and PE in adults.	28 July 2014

DVT: Deep vein thrombosis                      SE: Systemic Embolism  
NVAF: Non-valvular atrial fibrillation        TIA: Transient Ischaemic Attack  
NYHA: New York Heart Association            VTE: Venous Thromboembolic Events  
PE: Pulmonary Embolism

## 2. STUDY OBJECTIVES AND ENDPOINTS

The overall objective of this study is to describe the utilization pattern of apixaban in Sweden.

Specifically, the study seeks to:

1. ***Estimate*** the proportion of apixaban users in the outpatient settings who receive the drug for the approved indications at the time of the study,
2. ***Describe*** the characteristics of the patients who are prescribed apixaban for on-label and off-label indications.

## 3. STUDY DESIGN

This will be a descriptive study using retrospectively collected data from electronic health record databases. The study will describe the utilization pattern of apixaban during the first three years after launch for the VTE prevention indication in Sweden (01 Jan 2012 through 31 Dec 2014).

## 4. STUDY POPULATION

### 4.1. Inclusion Criteria

All patients identified in the database who have received an apixaban dispensation during the study period (01 Jan 2012 through 31 Dec 2014) will be included in this study.

### 4.2. Exclusion Criteria

There is no exclusion criterion. All patients identified in the database who have received at least one apixaban dispensation during the study period will be included.

## 5. STUDY TREATMENT AND DURATION

This is a descriptive study assessing the utilization pattern of apixaban in real-world outpatient settings. There is no study mandated dosing or duration requirement.

## 6. STUDY PROCEDURES

### 6.1. Data Source

Patients using apixaban will be identified from the National Prescribed Drug Register (PDR) which contains information on all drugs prescribed in Sweden that are dispensed to patients outside hospitals, including information about patients, drugs by ATC codes, dates, settings of the dispensing, and the specialty of the prescribing physician.

Relevant clinical history for the apixaban users identified from the PDR will be obtained from the National Patient Register (NPR). Patients in the PDR who have used apixaban will be linked to the NPR by a personal identification number (PIN) unique to all Swedish citizens. The NPR contains data from all hospital admissions in Sweden from 1987 to present. At each discharge, information is collected about the patient's demographics, primary and secondary diagnoses, procedure codes, hospitals and wards of admission, and dates of admission and discharge. Patients who have undergone knee or hip replacement surgery will be identified by applicable procedure codes and relevant ICD-10 diagnostic codes. The ICD-10 classification system was used from 1997 and onwards so data on diagnoses and procedures may extend back to 1997.

Since 2001, it is also possible to collect the same information from visits to hospital outpatient offices. Information about other diagnoses (eg, atrial fibrillation) in patients admitted to the hospitals without knee or hip replacement or visiting hospital outpatient offices will also be retrieved. The register is updated annually and data from the previous year is usually available for analyses in November each year after completion of data quality checks.

The databases cover the whole Swedish population of 9.3 million inhabitants. In 2008, about 14,500 knee and hip replacement surgeries and 4,600 hemi-hip arthroplasties were performed; 78% of the procedures were performed for primary arthrosis. The number of primary TKA was 10,600 in 2008. In addition, re-operations and revisions were also performed. Following an average hospital stay of 4 days, 25% of the patients are discharged to rehabilitation centers or nursing homes and 75% of the patients are discharged to home. The total number of hip arthroplasties increased by 10% from 2008 to 2010.

Inpatient and outpatient hospital data are available through the NPR, but the register does not include information from primary care visits. To address the missing primary care data, a sensitivity analysis will examine primary care records for apixaban users in Västra Götaland County (1.6 million, available from 2006). These regional data will supplement the nationwide data with greater detail for patients in Västra Götaland County, as well as provide an insight into the effect of missing primary care data. At this time, Västra Götaland is the only region in Sweden where primary care data are available. These records are based on patient contacts to primary care centers and collected in the health administrative databases.

The total number of persons diagnosed with atrial fibrillation and flutter in inpatient settings in 2010 was 25,672 (0.3%) according to national Swedish health statistics. The overall prevalence of atrial fibrillation has been studied in a geographically well-defined area of northern Sweden using data from a quality register of anticoagulant treatment and was found to be 2.5% in 2010 (Andersson, Londahl et al. 2012).

## 6.2. Data Compilation Procedure

Patients who received a dispensation for apixaban (identified by ambulatory prescriptions by general practitioner or specialist physician) will be identified. The personal identification numbers of these patients will be used to link to their hospital records.

Hip and knee replacement and other surgeries will be identified via appropriate procedure codes and ICD-10 codes from hospital discharge diagnoses. The following algorithm will be used to identify the patients who have undergone the elective hip or knee replacement surgery:

- First, procedure codes will be used to identify all patients who have undergone hip or knee replacement surgery within 30 days before apixaban prescription (including total and partial replacement procedures).
- Second, hospital discharge diagnoses (both primary and secondary) will be used to see if these included hip or knee fracture diagnostic codes.
  - If yes, then the hip or knee replacement surgery will be considered non-elective and apixaban prescription off-label.

If the primary or secondary discharge diagnoses do not include hip or knee fracture, then surgery will be considered elective and apixaban prescription on-label.

NVAF and treatment of DVT/PE will be identified by ICD-10 diagnosis codes in the main or secondary discharge diagnoses as well as in hospital outpatient visits and, where available, the primary care diagnoses.

[figure not shown]
### **6.3. Decision Rule for Defining On- and Off-label Use**

For the purpose of this study, apixaban prescriptions for the NVAF and treatment of DVT/PE indications will be considered off-label up to and including the date that apixaban received approval for those uses in the EU. Apixaban prescriptions for the NVAF and the treatment of DVT/PE indications will be classified as on-label starting on the day after regulatory approval and continuing through the end of the study.

On-label use of apixaban will be defined as a dispensation of the drug to:

1. An adult (ie, 18 years of age or older) and
2. A patient whose hospital records include:
  - a) An elective hip or knee replacement within 30 days before the apixaban prescription, or,
  - b) An apixaban prescription after 19 November 2012 and a diagnosis of NVAF before that apixaban prescription, or,
  - c) An apixaban prescription after 28 July 2014 and a diagnosis of DVT or PE before the apixaban prescription ([Figure 1](#)).

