## 7.2. Data Analyses

Descriptive analyses of patient level data will be conducted. Patients will be classified as on-label or off-label apixaban users based on their first prescription for apixaban. The demographic and clinical characteristics of patients identified to have received an apixaban dispensation will be described. The proportion of patients receiving the drug for indications within and outside the approved label in each of the study years will be estimated and any trend over time will be described. From the hospital discharge records, the comorbidities and clinical procedures (e.g., surgeries) at the time of or within 30 days prior to the off-label use will be tabulated as the possible indications for the off-label use. If discharge records during this period do not provide possible indications, information from previous discharges will also be tabulated according to the most recent diagnosis. Furthermore, possible switching from other antithrombotic treatment will be investigated based on dispensed prescriptions during the past year. The dose and duration of prescriptions will be summarized where available.

Stratified descriptive analyses by indication will be performed as described below. As the first step, the study will estimate the proportions of all patients in Swedish databases over the 3-years post-launch period who received apixaban for:

1. VTE prevention following elective hip and knee replacement surgery (on-label indication).
2. NVAf (off-label indication before the approval, and on-label following the approval).
3. Treatment of DVT/PE (off-label indication before the approval, and on-label following the approval).
4. Any other conditions from a list of pre-defined off-label indications, including other types of surgery and history of other diseases (off-label indications). These may include but will not be limited to hip fracture surgeries, general surgeries, gynaecologic and abdominal surgeries, and diagnoses such as cancer, myocardial infarctions, other cardiac conditions, and other hypercoagulable states in which apixaban could be used off-label.

5. Patients who have no evidence of the conditions for on-label use and who cannot be assigned to the list of pre-defined off-label uses will be classified as off-label and unknown.

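### The on-label rule for atrial fibrillation omits the risk-factor condition in the protocol's own statement of the indication, so on this criterion it can only overstate on-label use

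*Protocol*

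**What the plan says.** Section 1.1 of the Protocol gives the second approved indication as "Prevention of stroke and systemic embolism in adult patients with nonvalvular atrial fibrillation (NVAf) with one or more risk factors". Table 1 repeats the condition with examples: "Prevention of stroke and SE in adult patients with NVAf, with one or more risk factors, such as prior stroke or TIA", followed by age of at least 75 years, hypertension, diabetes and symptomatic heart failure.

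Section 1 describes off-label prescribing as possibly including "use in patients who do not meet age requirements, or other criteria as outlined in the label". Objective 1 in Section 2 is to estimate "the proportion of apixaban users in the outpatient settings who receive the drug for the approved indications".

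The decision rule in Section 6.3 requires an adult who meets one of three routes. Route (b) reads "An apixaban prescription after 19 November 2012 and a diagnosis of NVAF before that apixaban prescription". It has no risk-factor test. Section 6.2 identifies the condition by code alone: "NVAF and treatment of DVT/PE will be identified by ICD-10 diagnosis codes in the main or secondary discharge diagnoses", together with hospital outpatient diagnoses and, where available, primary care diagnoses. Item 2 of the strata in Section 7.2 divides the group by date alone: "NVAf (off-label indication before the approval, and on-label following the approval").

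**The concern.** The objective and the decision rule define different quantities. Under Sections 1.1 and 2, the numerator is use within an indication that carries a risk-factor condition. Under Section 6.3(b), it is use after a diagnosis and after a date. Someone with NVAF and no risk factor is outside the first and inside the second.

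This matters for two reasons. First, the study exists because the sponsor regards use outside the approved indications as a concern, and this is one such use. Second, atrial fibrillation is the largest projected group: Section 7.1 projects up to 13,000 such patients in a total of 19,000, against about 600 for VTE prevention.

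The omission does not look like a declared simplification. Other qualifiers of the label are enforced: adult age in Section 6.3, and elective surgery through a two-step procedure-and-fracture-code algorithm in Section 6.2. Section 10.2 does not list the missing condition as a limitation.

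**Working it through.** **1. The texts side by side.** Take an adult under 75 with a coded NVAF diagnosis, a first prescription after 19 November 2012 and no stroke risk factor.
- Section 1.1 and Table 1: outside the indication, because no risk factor is present.
- Section 1: failing a label criterion is an example of off-label prescribing.
- Section 6.3(b): on-label.
- Section 7.2, item 2: on-label, because the prescription follows approval.

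No readable text restores the condition. The error from this element runs one way: it can add patients to the on-label count but cannot remove any.

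**2. The Protocol's precision figures (Table 2).** Full width of a 95% Wald interval: 2 × 1.96 × √(p(1 − p)/19,000).

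| Off-label % | Table 2 width (points) | Recomputed (points) |
|---|---|---|
| 5 | 0.6 | 0.62 |
| 15 | 1.0 | 1.02 |
| 25 | 1.2 | 1.23 |
| 35 | 1.4 | 1.36 |
| 45 | 1.4 | 1.42 |

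All five entries reproduce, so the precision table is not in question.

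**3. Size of the shift.** Inputs from Section 7.1: at most 13,000 atrial fibrillation patients and 19,000 in total, so 13,000/19,000 = 68.4%. The share f of NVAF users with no risk factor is not in the Protocol and is assumed. Patients affected = 13,000 × f. Shift = 13,000 × f / 19,000.

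| Assumed f | Patients | Shift (points) |
|---|---|---|
| 1% | 130 | 0.68 |
| 2% | 260 | 1.37 |
| 5% | 650 | 3.42 |
| 10% | 1,300 | 6.84 |
| 15% | 1,950 | 10.26 |

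Each row is an upper value for its f. The 13,000 is a projected maximum. It counts atrial fibrillation rather than NVAF. It covers 2012 to 2014, so it includes any use up to the approval date, which is already off-label. Some patients may also qualify through route (a) or (c).

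**4. Share at which the shift matches the stated precision, at 25% off-label.**
- Half-width, 0.616 points: f = 0.00616 × 19,000 / 13,000 = 0.9%.
- Full width, 1.231 points: f = 0.01231 × 19,000 / 13,000 = 1.8%.

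**The case against.** **The abbreviation may carry the condition.** Section 1.1 and Table 1 use NVAF as the short name of the full indication, and Section 6.4 leaves operational definitions and coding to the SAP. On that view the risk-factor test could be built into the term. This softens the point but does not remove it. Section 6.3(b) asks for a diagnosis, not for the indication, and Section 6.2 finds that diagnosis by ICD-10 code. The classification rule itself is fixed in the Protocol.

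**A strict test would bring its own error.** This stands. Primary care data exist for one county only (Section 6.1), NYHA class is not among the data elements (Section 6.4), and a dispensed drug does not establish a diagnosis. Requiring a recorded factor would push some patients who truly meet the indication out of the on-label count. This argues for showing two figures, not for leaving the condition out.

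**The size is assumed.** This also stands. If the share is below about 0.9%, the shift is smaller than the CI half-width at 25% off-label.

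Three stronger readings are tempting, and the Protocol does not support them.
- *The reported on-label proportion is biased upward overall.* Patients whose qualifying diagnosis is recorded only in primary care are missed outside one county, which lowers apparent on-label use. The net direction is unknown.
- *A patient with none of the five Table 1 factors is off-label.* Table 1 introduces them as examples, so the list is open.
- *Such use would be wholly hidden.* Section 7.2 plans demographics, concomitant medication and selected comorbidities within each indication stratum. The comorbidities it names (renal, hepatic, bleeding) are not the stroke risk factors, so the cover is partial, but it is not nil.

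**Conclusion.** The contradiction is real and rests on the Protocol's text alone: Section 6.3(b) and item 2 of Section 7.2 do not implement the indication stated in Section 1.1 and Table 1. On this criterion the rule can only overstate on-label use.

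How far cannot be determined from the Protocol. For an assumed 1% to 15% of NVAF users without a risk factor, the overstatement is at most about 0.7 to 10.3 points, taking the maximum of 13,000 patients and treating all as prescribed after approval. A share above about 1.8% would be enough, on those assumptions, for the definitional error to exceed the 1.2-point interval width stated for 25% off-label use. These figures are illustrative upper values, not estimates of the bias in the study's result.

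Figure 1 is not shown and was not checked.

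**What to change.** - Reconcile Section 6.3(b) and item 2 of Section 7.2 with Table 1, and Figure 1 if it repeats the rule. Split post-approval NVAF users into those with a recorded risk factor and those with none recorded.
- Derive the split from age, ICD-10 codes and dispensed drugs, all already listed in Section 6.4. Treat the Table 1 factors as examples and pre-specify any others to be accepted.
- Report the on-label proportion twice, excluding and including the group with no recorded factor, as lower and upper bounds for this criterion. The lower figure is a bound only so far as a recorded factor, especially one inferred from a drug, is a true one.
- Use the Västra Götaland primary care records, already planned for a sensitivity analysis, to gauge how often a risk factor is missed in hospital data.
- State the limits in Section 10.2: no primary care data elsewhere and no NYHA class.

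The cost is a wording change, one derived variable from data already collected and one extra row in the tables. Section 7 asks that major modifications be reflected in a protocol amendment, and a change to the classification rule would reasonably count as one. The downside is that some patients with unrecorded risk factors will fall in the second group, which is why both figures are shown.

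### From 20 November 2012 to 28 July 2014, any earlier NVAF code makes a start on-label even when a DVT or PE was recorded just before it, and the planned tables would not show such starts

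*Protocol*

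**What the plan says.** Section 6.3 of the protocol joins its three on-label criteria with 'or'. Only the surgery criterion limits recency: "An elective hip or knee replacement within 30 days before the apixaban prescription, or". The NVAF criterion is "An apixaban prescription after 19 November 2012 and a diagnosis of NVAF before that apixaban prescription", and the DVT/PE criterion is "An apixaban prescription after 28 July 2014 and a diagnosis of DVT or PE before the apixaban prescription". Both require the diagnosis to come first, but neither says how recent it must be. Section 6.1 notes that "data on diagnoses and procedures may extend back to 1997".

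The lead-in to 6.3 sets status by indication and date: prescriptions for NVAF and for DVT/PE treatment "will be considered off-label up to and including the date that apixaban received approval for those uses in the EU". Section 7.2 follows the same logic in its strata. Item 2 is "NVAf (off-label indication before the approval, and on-label following the approval" and item 3 is "Treatment of DVT/PE (off-label indication before the approval, and on-label following the approval".

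Each patient has one status: "Patients will be classified as on-label or off-label apixaban users based on their first prescription for apixaban". Section 7.2 also tabulates comorbidities and procedures from the 30 days before the start as possible reasons for use, but only for off-label use.

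**The concern.** The data elements in section 6.4 include no recorded reason for prescribing, so the indication has to be inferred from diagnosis codes. When a patient has codes for two indications and only one is approved at the time, the result depends on how the codes are combined. Under 6.3(b) an NVAF code of any age is enough, and a DVT or PE recorded shortly before the start has no influence on the status.

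Treatment of DVT/PE before its approval is one of the off-label uses that 7.2 sets out to count. Starts of this kind in patients with an NVAF code would go into the on-label total. The planned output would not bring them to light, for two reasons:

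- The 30-day tabulation starts from off-label users.
- The comorbidity summary within each stratum covers selected conditions. Its named examples do not include DVT or PE, and it has no recency window.

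Any error goes one way, towards too little off-label use, and a larger sample does not reduce it.

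**Working it through.** **1. The rules applied to a patient with NVAF and DVT/PE both recorded before the first prescription**

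| First prescription | 6.3(b) | 6.3(c) | Status by 6.3 | 7.2 item 2 | 7.2 item 3 |
|---|---|---|---|---|---|
| 1 Jan 2012 to 19 Nov 2012 (324 days) | not met | not met | off-label* | off-label | off-label |
| 20 Nov 2012 to 28 Jul 2014 (616 days) | met | not met | on-label | on-label | off-label |
| 29 Jul 2014 to 31 Dec 2014 (156 days) | met | met | on-label | on-label | on-label |

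*Unless the surgery criterion (a) is met.

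The days sum to 324 + 616 + 156 = 1,096, the whole study period. For NVAF, the strata carry different labels only in the middle row.

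**2. The plan's own precision figure**

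Table 2 gives a 95% CI width of 1.2 points at 25% off-label with 19,000 patients. Check: 2 × 1.96 × √(0.25 × 0.75 / 19,000) = 0.0123, or 1.23 points. The figure is reproduced, and the half-width is about 0.62 points. The other four rows also reproduce (0.62, 1.02, 1.36 and 1.42 against the stated 0.6, 1.0, 1.4 and 1.4).

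**3. Size of the affected group**

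From the documents (section 7.1): up to 13,000 AF patients and 19,000 patients in total.

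Assumed, because the documents do not give them:

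- *Share of AF patients who start in the 616 days: 50% to 80%.* An even spread from 20 November 2012 to 31 December 2014 (772 days) gives 616 / 772 = 0.798. The 50% stands for uptake weighted towards the end of the study.
- *Share of those starters with a DVT/PE code in the prior 30 days: 1% to 3%.*

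Patients affected = 13,000 × share starting in the period × share with a recent code.

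- Low: 13,000 × 0.50 × 0.01 = 65, and 65 / 19,000 = 0.34 points.
- High: 13,000 × 0.798 × 0.03 = 311, and 311 / 19,000 = 1.64 points.

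The shift equals the half-width at 0.0062 × 19,000 ≈ 117 patients. That is 117 / 6,500 = 1.8% of starters in the low-uptake case, or 117 / 10,374 = 1.1% in the high-uptake case.

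**4. The surgery criterion**

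The same overlap can arise under 6.3(a), when a DVT or PE follows an elective replacement and apixaban is started within 30 days of the surgery. It can occur from 1 January 2012 to 28 July 2014 (940 days). Section 7.1 expects about 600 such patients in the whole study. Even at 3%, that is 18 patients, and 18 / 19,000 = 0.09 points, which is negligible.

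**The case against.** The strongest reply is that 6.3 is the decision rule and gives one answer. Its criteria are alternatives, so a patient who meets (b) is on-label, and 7.2 allows one status per patient. Items 2 and 3 of 7.2 describe what the drug was received for, with the status of that indication by date. A clash arises only if someone already on-label by 6.3 is placed in item 3. Item 5, which begins from patients without evidence for on-label use, fits a scheme in which the on-label criteria are checked first. Figure 1 is cited directly after criterion (c) and may set the order, and section 6.4 leaves operational definitions to the SAP. All of this stands. A reader might infer a flat contradiction that gives one patient two labels; the documents support only an overlap between the rule and the strata that the readable text leaves unresolved.

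Three other stronger readings also fail:

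- *That the conflict covers the whole time before DVT/PE approval.* Up to and including 19 November 2012, NVAF is off-label as well, so the two strata agree.
- *That timing is ignored.* The diagnosis must precede the prescription and the prescription must follow approval. Only recency is missing from (b) and (c).
- *That any DVT/PE code since 1997 could turn an AF patient off-label, giving a much larger group.* This needs an order that puts DVT/PE ahead of NVAF. The readable text states none, and the 'or' in 6.3 points the other way.

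It is also fair that the 30-day window in 7.2 serves to describe off-label use and not to classify it, and that a DVT/PE code within 30 days does not prove why the drug was started.

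What the reply does not answer is visibility. An order in Figure 1 or the SAP would settle where these patients go, but it would not show how far the on-label proportion depends on them.

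**Conclusion.** The point holds as a gap in what the analysis can reveal. For first prescriptions from 20 November 2012 to 28 July 2014, an NVAF code of any age makes a start on-label despite a recent DVT or PE, and no planned table identifies those starts. Off-label DVT/PE use may therefore be understated.

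Under the stated assumptions the effect is 65-311 patients, or 0.3-1.6 points of the on-label proportion. The low end lies below the planned half-width of about 0.6 points and the high end is well above it. The range rests on co-diagnosis and uptake shares that are not in the documents, and on a projection of 13,000 that is an upper figure for AF rather than NVAF. It shows scale and is no estimate of bias, since some of these patients will have started apixaban for NVAF. The contribution of hip and knee patients is negligible.

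This is a worthwhile, inexpensive improvement. It does not show that the main rule is wrong.

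**What to change.** Keep 6.3 as the main rule. State in 7.2 which single stratum holds a patient with both NVAF and DVT/PE, in agreement with 6.3 and Figure 1.

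Add one sensitivity analysis for first prescriptions up to 28 July 2014:

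- Flag patients who are on-label by (b) and have a DVT/PE diagnosis in the 30 days before that prescription. For completeness, also flag those on-label by (a) whose DVT/PE is dated after the surgery and falls in the same 30 days.
- Report their number.
- Give the on-label proportion twice, with these patients counted once as on-label and once as off-label.

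The dates needed are already among the data elements in section 6.4. The cost is a few lines of text, one extra table row and a small range beside the main figure. The flag is a proxy for the reason for starting, and the report should say so.

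### Criterion (c) in Protocol 6.3 sets no look-back for DVT/PE, so for late-2014 starters it cannot separate treatment or recurrence prevention from mere history, and no planned analysis shows how much this matters.

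*Protocol*

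**What the plan says.** Protocol 6.3 gives three routes to on-label status for an adult:

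- (a) "An elective hip or knee replacement within 30 days before the apixaban prescription"
- (b) "An apixaban prescription after 19 November 2012 and a diagnosis of NVAF before that apixaban prescription"
- (c) "An apixaban prescription after 28 July 2014 and a diagnosis of DVT or PE before the apixaban prescription"

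Only (a) carries a time window. On the depth of history, section 6.1 says "data on diagnoses and procedures may extend back to 1997". On the source of codes, section 6.2 says "NVAF and treatment of DVT/PE will be identified by ICD-10 diagnosis codes in the main or secondary discharge diagnoses", and it adds hospital outpatient visits and, where available, primary care.

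Table 1 gives the approved indication as "Treatment of DVT and PE, and prevention of recurrent DVT and PE in adults", with no stated limit on time since the event. Section 7.2 fixes each patient's class by the first apixaban prescription. For off-label users, it says that "the comorbidities and clinical procedures (e.g., surgeries) at the time of or within 30 days prior to the off-label use will be tabulated", and it turns to earlier discharges only if that window gives no possible indication.

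**The concern.** Elsewhere the protocol uses recency as evidence of why the drug was prescribed: 30 days for surgery in 6.3, and 30 days first when 7.2 looks for the reason behind off-label use. Criterion (c) does not use it. A single secondary code from 1998 is enough to make a first prescription in September 2014 on-label.

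Take a patient with that code, no anticoagulant dispensed for years, and a general or gynaecological operation two weeks before the prescription. Such operations are on the off-label list in 7.2. The rule still classes the patient as on-label. Because the 30-day tabulation is defined for off-label use, the operation does not appear there.

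Two things are at stake. The on-label proportion (objective 1) may be too high through this clause. The profile of the DVT/PE stratum (objective 2: demographics, comorbidity, dose, duration) may mix patients under treatment or recurrence prevention with patients who only have a history.

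**Working it through.** **1. The plan's own precision figures.** Protocol Table 2 assumes N = 19,000. The full width of the 95% CI is 2 × 1.96 × √(p(1 − p)/19,000).

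| Off-label % | Recomputed width (points) | Table 2 |
|---|---|---|
| 5 | 0.62 | 0.6 |
| 15 | 1.02 | 1.0 |
| 25 | 1.23 | 1.2 |
| 35 | 1.36 | 1.4 |
| 45 | 1.42 | 1.4 |

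Table 2 reproduces. It covers sampling error only. The half-width at 25% is 1.231/2 = 0.62 points, or 0.00616 × 19,000 ≈ 117 patients.

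**2. Who is exposed.** Criterion (c) applies from the day after approval. From 29 July to 31 December 2014 is 156 days. The study period, 1 January 2012 to 31 December 2014, is 1,096 days, and 156/1,096 = 14.2%. Uptake need not be even, so this is a share of calendar time and not of patients. Only patients who do not already qualify under (a) or (b) are affected. A 1997 code is about 17 years old in 2014.

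**3. Size of the effect.** Let f be the share of all users who are on-label only through (c). Let r be the share of those whose old code reflects neither treatment nor prevention of recurrence. The on-label share is raised by f × r. The protocol gives neither quantity, so both ranges are assumptions. Section 7.1 projects about 600 surgical and up to 13,000 AF patients, which leaves at least 19,000 − 600 − 13,000 = 5,400 for everything else over three years. A range of 1% to 10% (190 to 1,900 patients) is compatible with that but not derived from it.

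| f | r = 10% | r = 25% | r = 50% |
|---|---|---|---|
| 1% | 0.1 points (19 patients) | 0.25 (48) | 0.5 (95) |
| 2% | 0.2 (38) | 0.5 (95) | 1.0 (190) |
| 5% | 0.5 (95) | 1.25 (238) | 2.5 (475) |
| 10% | 1.0 (190) | 2.5 (475) | 5.0 (950) |

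The effect passes the 0.62-point half-width when f × r exceeds about 0.62%. That requires r above 0.616/1 = 62% at f = 1%, 31% at f = 2%, 12% at f = 5%, and 6% at f = 10%.

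Among users who qualify only through (c), the contamination is r itself, whatever f is.

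**4. Would a planned analysis show it?** The one sensitivity analysis in 7.2 adds primary care diagnoses in Västra Götaland. Adding codes can create further routes to on-label status under (b) and (c), but it cannot expose a code that is too old to be relevant. Section 10.2 names missing diagnoses as a limitation, not outdated ones.

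**The case against.** The strongest reply is the label itself. Table 1 includes prevention of recurrence with no time limit, and a past DVT or PE is exactly what such a patient has. This stands. A reader might infer that any old code is a false on-label classification, or that DVT/PE should be read as acute only; the documents do not support that. It also weakens the contrast with the 30-day surgical window, because surgical prophylaxis is tied to one operation. Criterion (b) has no window either. What remains is that the rule cannot tell the two kinds of patient apart.

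A reader might also infer that the study overstates on-label use overall. The documents do not show this. Sections 6.1 and 10.2 acknowledge that primary care diagnoses are missing outside one county, which pushes measured on-label use down. The net direction is open.

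A third tempting inference is that old codes also hide recent procedures in patients who started before 28 July 2014. This is not supported. Those patients are off-label under 6.3, so they cannot raise the on-label share, and 7.2 tabulates their 30-day procedures first. No stated precedence lets an old DVT code override a recent procedure.

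Finally, 6.4 leaves operational definitions to the SAP, and 7.2 already plans to describe anticoagulant history in every stratum, so part of the problem would be visible. But 6.3 fixes the decision rule itself without a window, and a stratum-level summary does not carry through to the on-label proportion. Figure 1, to which (c) refers, is not legible in the copy reviewed. If it shows a window, the text of 6.3 should say so.

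**Conclusion.** The point holds in a limited form. For first prescriptions from 29 July to 31 December 2014 that do not qualify under (a) or (b), criterion (c) does not separate treatment or recurrence prevention from mere history, and it keeps recent procedures on the off-label list out of view in those patients. Through this clause alone, the on-label share may be too high and cannot be too low; the net error of the study is not established.

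The size cannot be computed from the protocol. Under the assumed ranges for f and r it runs from 0.1 to 5.0 points, so it may be negligible or may exceed the sampling error in Table 2 several times over. The data to find out are already being collected. This is a cheap improvement, not a flaw that invalidates the main estimate.

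**What to change.** Keep the 6.3 rule for the main estimate. In 7.2, split the users who are on-label only through (c) into three groups: recent DVT/PE code; older code with an anticoagulant dispensed in the past year (the period 7.2 already uses for switching); and older code only. Then:

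- report the time from the last DVT/PE code to the first apixaban prescription;
- tabulate procedures and diagnoses in the prior 30 days for the older-code-only group, as for off-label users;
- give the overall on-label proportion with that group counted as on-label and as off-label;
- repeat this over more than one look-back window, for example 6, 12 and 24 months, since the documents support no single cut.

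The cost is wording in 7.2 and a few extra table rows. Diagnosis dates, procedures and dispensing records are already listed in 6.4. Some true recurrence-prevention patients restarting after a gap will fall in the older-code-only group. That is why the group should not simply be moved to off-label, and why the proportion is reported both ways.
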